#### 3.3 Outcome Measures:

#### 3.3.1 Primary Outcome Measure

• Rates of grade 3 acute GI and hematologic toxicity (as raw percentage)

#### 3.3.2 Secondary Outcome Measures

• Late (> 3 months after treatment) toxicity rates (as raw percentage), as related to the RTOG Late Radiation Toxicity Grading Scale.

- One-year rates of overall, progression-free, and metastasis-free survival (will
  continue to obtain data on these outcomes at subsequent visits beyond 1
  year, but the 1 year time point will represent the outcome measure of
  interest)
- Pain control at one and three months after treatment (based on reporting of standard pain score (0-10) with an option to record pain score based on FACES assessment scale) –will continue to obtain data on pain control at subsequent visits but these 2 time points will represent the main outcome measures of interest
- Quality of life at each follow-up visit (measured by EORTC QOL-Q scale) will
  continue to obtain data on quality of life at subsequent visits but these 2 time
  points will represent the main outcome measures of interest

# 4. ELIGIBILITY CRITERIA

#### 4.1 Inclusion Criteria

- Age  $\geq$ 18 years.
- Karnofsky Performance Status >70% (see Appendix II).
- Histologically confirmed adenocarcinoma of the pancreas or ampulla of Vater; at least the majority of the histopathologic specimen must be identified as adenocarcinoma as opposed to another histologic subtype. In patients with a diagnosis of recurrent disease (based on radiographic progression and/or rising CA19-9 levels) and a history of a biopsy-proven adenocarcinoma of the pancreas or the ampulla of Vater, repeat biopsy of the recurrence site is not required for participation of the trial.
- Pancreatic or periampullary tumors must be less than 8.0 cm in greatest axial dimension at the time of treatment planning.
- Patients who have been treated with any combination of surgical resection and neoadjuvant/adjuvant conventional chemoradiation therapy for resectable disease or conventional chemoradiation as definitive treatment for unresectable or borderline resectable disease are eligible for the study, provided that at least 180 days have elapsed since completing any previous radiation treatment. Patients who have been receiving continued chemotherapy following their initial radiation treatment are eligible regardless of when the most recent chemotherapy was received. Those patients who have received prior radiation therapy will constitute Cohort A and will receive SBRT as 5 Gy x 5.
- Patients who have not previously undergone radiation therapy can have a history of treatment with either chemotherapy (for unresectable/borderline resectable disease) or any combination of surgery and chemotherapy (for resectable disease). Patients with no history of prior radiation treatment will constitute Cohort B and will receive SBRT as 6.6 Gy x 5. Please note that patients must have received at least two cycles of chemotherapy (with selection of drugs at the discretion of the treating oncologist) before SBRT treatment on protocol.
- Acceptable organ and marrow function as defined below (taken no earlier than time of CT Simulation, within 3 weeks prior to radiotherapy):
  - Leukocytes >3,000/μL

- O Absolute neutrophil count >1,500μL
- $\circ$  Platelets > 100,000/ $\mu$ L
- o Total Bilirubin ≤1.5x institutional upper limit of normal
- AST(SGOT)/ALT(SGPT) <2.5x institutional upper limit of normal
- Creatinine ≤ institutional upper limit of normal OR creatinine clearance >60 mL/min/1.73 m² for patients with creatinine levels above institutional normal
- Ability to understand and the willingness to sign a written informed consent document.
- Life expectancy > 3 months.
- Radio-opaque markers must be present within the tumor bed. In patients who
  have undergone surgical resection, radio-opaque surgical clips within the tumor
  bed can be used as fiducials. Patients without surgical clips in the tumor bed
  must be able to have fiducials placed endoscopically, laparoscopically, or
  through a CT- or ultrasound-guided technique. If not, the tumor must be
  posterior and adjacent to the aorta, and treatment will only be permitted at the
  discretion of the Principal Investigator.

# 4.2 Exclusion Criteria

- Age < 18 years.
- Uncontrolled intercurrent illness including, but not limited to, ongoing or active
  infection (or infections requiring systemic antibiotic treatment), active upper GI
  ulceration or hemorrhage, symptomatic congestive heart failure, unstable angina
  pectoris, cardiac arrhythmia, or psychiatric illness/social situations that would
  limit compliance with study requirements.
- Any concurrent malignancy other than non-melanoma skin cancer, non-invasive bladder cancer, early stage prostate cancer, or carcinoma in situ of the cervix.
   Patients with a previous non-pancreatic, non-periampullary malignancy without evidence of disease for > 5 years will be allowed to enter the trial.
- Pregnant and breastfeeding women are excluded as are women of child-bearing
  potential who are unwilling or unable to use an acceptable method of birth
  control (hormonal or barrier method of birth control; abstinence) to avoid
  pregnancy for the duration of the study. Should a woman become pregnant or
  suspect she is pregnant while participating in this study, she should inform her
  treating physician immediately.
- Women who are not post-menopausal (as defined in Appendix III) and have a positive urine or serum pregnancy test or refuse to take a pregnancy test.
- Patients with a life expectancy of < 3 months.
- Patients with metastatic disease.
- Patients with evidence of gross tumor invasion into the lumen of the stomach or small bowel are not eligible; if imaging suggests luminal invasion of tumor, this must be ruled out endoscopically before the patient can be enrolled on study.

# 5. STUDY DESIGN

This is a single center, single arm unblinded prospective study of the safety of pancreatic SBRT in patients with unresectable, borderline resectable, or recurrent pancreatic/periampullary cancers who have previously undergone treatment with chemotherapy, surgery, photodynamic therapy, conventionally fractionated radiation treatment, or any combination of these therapies.

#### 6. PATIENT REGISTRATION

Potential patients will be identified per the recommendation of surgeons or GI Combined Modality Tumor Board or equivalent combined modality assessment. Potential patients will be recruited through self-referral and the advice of their attending physician. No advertisement will be used to recruit subjects. This trial will be registered at clinicaltrials.gov.

Patients who appear to be eligible for this trial will undergo the Informed Consent Process and be screened for eligibility utilizing the Eligibility Criteria. Consent will be obtained after a clear and thorough discussion between the patient and the Principal Investigator or any of the co-investigators in clinic. Eligible patients who complete the Informed Consent Process will be registered in the OnCore® database and assigned a patient ID number. Regulatory files will be maintained by the Radiation Oncology Research Office or the IU Simon Cancer Center Clinical Trials Office. Applicable regulatory documents must be completed and on file prior to registration of any patients.

# 7. SBRT ADMINISTRATION AND RADIATION TREATMENT

# 7.1 Pre-Linac-based SBRT Tests, Procedures, and Planning

The following will be completed prior to Linac-based SBRT:

- Medical history and clinical examination.
- CBC with differential, chemistry panel, and CA19-9 measurement.
- Gold fiducial seed placement percutaneously, intraoperatively, or under endoscopic ultrasound guidance, which may be performed prior to enrollment.
- Pathologic confirmation of malignancy. (Core biopsies may be obtained during gold fiducial placement as needed; however, repeat biopsy is NOT required for study enrollment in patients who already have pathologically proved adenocarcinoma of the pancreas or periampullary region.)
- Pancreatic-protocol CT or CT of the chest/abdomen/pelvis
- Baseline FDG-PET/CT (dual phase) may be obtained for tumor staging and treatment planning purposes; however, patients who are unable to undergo PET CT scanning (e.g., due to insurance refusal of coverage) can still participate in the study.
- Signed informed consent document.
- Baseline collection of EORTC QLQ C-30/ PAN26 QOL.

#### 7.1.1 Fiducials

Treatment on this protocol requires placement of 1-5 gold (99.9% pure, 1-5 mm length, or visicoils) fiducials for targeting purposes. The fiducials will be used as surrogates for targeting the daily tumor position during treatment. The fiducials will be placed directly into the tumor and/or periphery under endoscopic ultrasound or

CT guidance. When possible, clips or fiducials will also be placed in the proximal duodenum directly adjacent to the pancreatic tumor. Fiducials may be implanted prior to enrollment, as this is an acceptable standard of care procedure for any patient receiving radiotherapy for locally advanced pancreatic or periampullary cancer. Patients who have undergone surgical resection or attempted surgical resection may already have clips or fiducials in the tumor bed, which are acceptable markers for the purposes of this study.

If fiducials are not placed intraoperatively and/or prior to enrollment, placement will be done and is expected to be done on an outpatient basis. In rare occurrences when fiducials/clips cannot be placed, patients may be treated at the discretion of the PI.

#### 7.1.2 Simulation

Simulation should be done following placement of fiducials; however, this may vary and is at the discretion of the principal investigator. Patients will be positioned supine in a standard custom immobilization device. Standard free-breathing CT and respiratory-correlated 4-D pancreatic protocol CT will be obtained on each patient. The 4D-CT scan will be used for characterizing target motion during quiet respiration. For more accurate tumor delineation, an arterial phase pancreatic protocol CT may be obtained (typically during expiration breath hold, 1.25 mm slices). Fiducial to fiducial fusions between these scans should be utilized whenever possible. The simulation scan should include T4/T5 to L5/S1 (upper abdomen).

IV and oral contrast must be used for simulation, unless the patient has an allergy that cannot be adequately premedicated. In these situations, the plan should be fused with a contrast-enhanced CT scan or MRI (ideally in a similar treatment position).

Motion management can be addressed using respiratory gating, breath-hold, or respiratory tracking. Fluoroscopy will be used to assess the motion of the implanted gold fiducials during simulation. If the fiducial motion is greater than 5 mm, then the Varian Respiratory Management (RPM) system will be utilized for treatment delivery in either the breath hold or respiratory gating modes (dependent on patient's ability to comply with breath hold). If motion is less than 5 mm, an internal target volume (ITV) will be generated based on the 4-D CT scan, and no respiratory management will be required during radiation treatment. As long as the specified dosimetric parameters for SBRT are reached, patients may be treated on any IGRT-enabled linear accelerator. All patients must start Linac-based SBRT within 4 weeks of the simulation scan.

# 7.1.3 Treatment Planning

When available, an FDG-PET scan can be used for treatment planning purposes and will be acquired on a flat table top with the same immobilization devices used for the simulation CT scan to enable accurate image fusion. An SBRT treatment plan will be developed using the Eclipse treatment planning system, based on tumor geometry and location. All treatment plans will be stored in their entirety on the Radiation Oncology Eclipse Servers for future reference. Institutional standards for radiation quality assurance and radiation delivery will be utilized. Target volumes will be contoured on the treatment planning CT by an attending physician in

radiation oncology at the IU Simon Cancer Center. Data from prior diagnostic CT scans, respiratory-correlated 4D-CT scan, and/or the FDG-PET/CT scan may be used to assist in treatment planning. The following three target volumes will be contoured:

- 1) **Gross tumor volume (GTV)**. This will consist of all visible tumor based on the free-breathing, IV contrast-enhanced CT scan. Data from the FDG-PET scan may be used to assist in contouring this volume if the patient has undergone a PET scan.
- 2) **Tumor-vessel interface (TVI)**. This will include the entire circumferential contour of any major upper abdominal blood vessel [including the portal vein (PV)], superior mesenteric artery/vein (SMA/SMV), celiac artery (CA), and/or common hepatic artery (CHA)] that is in direct contact with the tumor. The craniocaudal extent of the TVI contour should match that of the GTV for any vessel that is included in the TVI.
- 3) **Tumor-gut interface (TGI)**. This volume is defined as GTV or TVI that directly abuts the stomach, duodenum, small bowel, or large bowel. It will be delineated by creating a planning organ at risk volume (gut PRV) that will consist of the stomach, duodenum, small bowel, and large bowel plus a 3-mm expansion margin. Any areas of the GTV-PTV or the TVI-PTV that overlap with the gut PRV will be considered as TGI.

Table 2. Target volume expansion guide.							
Target Volume Base Structure Dose Expansion							
TGI	GTV (minus gut PRV)	30 Gy (6 Gy x 5)	n/a				
GTV-PTV	GTV	33 Gy (6.6 Gy x 5)	3 mm				
TVI-PTV	TVI	36 Gy (7.2 Gy x 5)	3 mm				

The final PTV (planning treatment volume) expansion will consist of an additional 3 mm of margin expansion to the GTV and TVI, except if the margin results in expansion into the duodenum or stomach. In these cases, margin expansion is allowed to be non-uniform. Please refer to Table 2. In patients who cannot tolerate or are otherwise not candidates for breath-hold radiation treatment (determination to be made at the discretion of the treating radiation oncologist), an internal target volume (ITV) for each of the above contours will be contoured based on the 4D CT scan in order to account for respiratory motion. The PTV expansion margins will then be added to the ITV in such cases. The dose will be prescribed to the isodose line that completely surrounds the PTV. It is recommended that 6-12 coplanar fields be used in the radiation treatment plan. Contours of the fiducials used for target localization will be generated on the applicable image sets for use in patient setup and treatment.

Radiation dose to the adjacent normal tissue will be minimized. Based on an analysis of duodenal toxicity representing pooled data from 3 previous prospective studies, the

following dose constraints must be met: V15< 9 cc, and V20< 3 cc. The duodenum, as defined for these dosing parameters, includes the entire duodenum on the same axial plane as the PTV and duodenum 1 cm above and 1 cm below the PTV. In patients who have undergone pancreaticoduodenectomy, the regions of the pancreaticojejunostomy, gastrojejunostomy, and hepaticojejunostomy that lie 1 cm above or below or lateral to the PTV will also be delineated as structures of interest. V15 and V20 are defined as the percent volume receiving 15 Gy and 20 Gy, respectively. No more than 1 cc of the proximal duodenum or proximal stomach may exceed 33 Gy for cohort B or 25 Gy for cohort A (reirradiation patients). Dose to the remainder of the normal tissues will be limited as follows:

- Liver (excluding tumor): 50% should be limited to <12 Gy (<8 Gy for cohort A/re-irradiation patients)
- Kidney: Combined volume for both should have 75% <12 Gy (<8 Gy for cohort A/re-irradiation patients)
- Stomach and duodenum: V15<9cc (V12<9 cc for cohort A) and V20<3cc (V15<3 cc for cohort A). 50% should be limited to <12 Gy (<8 Gy for cohort A). No more than 1 cc of proximal stomach can receive >33 Gy for cohort B, and no more than 1 cc of proximal stomach can receive >25 Gy for cohort A/re-irradiation patients.
  - Spinal cord: no more than 1cc can receive >8 Gy (>6 Gy for cohort A).
- No more than 1cc of the PTV can receive >130% of the prescription dose (4290cGy for 6.6Gy x 5; 3250cGy for 5Gyx5, cohort A).
- Greater than 90% of the PTV should receive 100% of the prescription dose (3300cGy for 6.6Gy x 5; 2500cGy for 5Gyx5).
- If the above constraints cannot be achieved, the dose to the TGI will first be decreased to from 30 to 25 Gy in 0.5 Gy increments. If the TGI dose is reduced to 25 Gy without meeting constraints, the dose to GTV-PTV will then be decreased from 33 to 25 Gy in 0.5-Gy increments. If constraints still cannot be met, then the TVI-PTV dose can be decreased in similar fashion. In such cases, 100% of the GTV-PTV and the TVI-PTV must receive at least 25 Gy (20 Gy for cohort A) (an allowed minor deviation, which will be documented). The highest dose that permits the above stomach and duodenal constraints to be achieved will be used. However, if even this constraint cannot be met, the patient should be removed from the protocol.

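### The tumor-gut interface row of Table 2 names tumor outside the gut margin, the opposite of the definition in the text, and should be corrected

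*Combined protocol and SAP*

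**What the plan says.** Everything at issue is in section 7.1.3 (Treatment Planning).

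- **Concept of the TGI, in the text:** "This volume is defined as GTV or TVI that directly abuts the stomach, duodenum, small bowel, or large bowel".
- **Delineation rule, in the text:** a gut PRV is made from stomach, duodenum, small bowel and large bowel plus 3 mm, and then "Any areas of the GTV-PTV or the TVI-PTV that overlap with the gut PRV will be considered as TGI".
- **Table 2, TGI row:** the base structure is "GTV (minus gut PRV" (closing bracket follows in the cell), the dose is 30 Gy in 5 fractions, and no expansion applies. The other rows are GTV-PTV (from the GTV, 33 Gy, 3 mm) and TVI-PTV (from the TVI, 36 Gy, 3 mm).
- **Step-down when constraints fail:** "the dose to the TGI will first be decreased to from 30 to 25 Gy in 0.5 Gy increments". GTV-PTV follows and then TVI-PTV, with the aim that "The highest dose that permits the above stomach and duodenal constraints to be achieved will be used". In such cases "100% of the GTV-PTV and the TVI-PTV must receive at least 25 Gy" (20 Gy for Cohort A).
- **Normal tissue:** stomach and duodenum have V15 and V20 limits of 9 cc and 3 cc in Cohort B, and "No more than 1 cc of the proximal duodenum or proximal stomach may exceed 33 Gy for cohort B". For small bowel beyond the duodenum and for large bowel there is no numeric limit, only the general statement "Radiation dose to the adjacent normal tissue will be minimized".

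**The concern.** The text and the table give two definitions of one dose-bearing volume, and they point in opposite directions. The text puts the reduced dose on target that touches or nearly touches gut. The table, taken literally, puts it on tumor clear of the gut and leaves the part next to gut under the 33 or 36 Gy rows. The first step-down would then lower dose to tumor where gut sparing is not the issue.

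This matters because the primary outcome (sections 3.1 and 11.9) includes acute grade 3 or greater GI toxicity, and late GI toxicity is a secondary objective (section 3.2). Table 2 is also the only place that sets each target volume beside its starting dose. No other section reconciles the two definitions.

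**Working it through.** **1. The plan's own figures.** Table 2 doses: 6 × 5 = 30 Gy, 6.6 × 5 = 33 Gy, 7.2 × 5 = 36 Gy. All three reproduce.

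**2. The two volumes.** Write PRV for the gut PRV.

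- Text: TGI = (GTV-PTV ∪ TVI-PTV) ∩ PRV, which lies wholly inside the PRV.
- Table: TGI base = GTV \ PRV, which lies wholly outside the PRV.

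Their intersection is empty whatever the anatomy. The table entry also omits the TVI and the 3 mm PTV margin, both of which the text includes.

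A numerical illustration on an assumed 1 mm voxel phantom (GTV of 15 mm radius, 14.1 cc; 3 mm PTV margin; one vessel; flat gut surface) gave:

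| Gut surface from GTV center (mm) | TGI by text (cc) | TGI by table (cc) | Shared (cc) |
|---|---|---|---|
| 14 | 2.74 | 13.3 | 0 |
| 16 | 1.53 | 13.9 | 0 |
| 18 | 0.64 | 14.1 | 0 |
| 20 | 0.11 | 14.1 | 0 |
| 25 | 0 | 14.1 | 0 |

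The sizes depend on the phantom; the zero does not. The last row shows that the literal table reading cannot be intended. With no gut nearby, the whole GTV becomes an interface at 30 Gy, while GTV-PTV, built on the same GTV, is prescribed 33 Gy.

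**3. Which reading is meant.** Three features fit the text and not the table: the name of the volume, its having the lowest of the three doses, and its being lowered first in a procedure driven by the stomach and duodenal constraints.

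**4. Size of the difference in Cohort B.** BED = D × (1 + d/(α/β)), with d = D/5. The α/β values of 10 (early) and 3 (late) are those of the protocol's Table 1.

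| Prescription | Early BED, α/β = 10 | Late BED, α/β = 3 |
|---|---|---|
| 30 Gy | 30 × 1.60 = 48.0 | 30 × 3.0 = 90.0 |
| 33 Gy | 33 × 1.66 = 54.8 | 33 × 3.2 = 105.6 |
| 36 Gy | 36 × 1.72 = 61.9 | 36 × 3.4 = 122.4 |

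The 33 Gy line matches Table 1 (54.8 and 105.6). Relative to 30 Gy:

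- Physical dose: 33/30 = 1.10 and 36/30 = 1.20, that is 3 or 6 Gy more.
- Early BED: 54.78/48.0 = 1.14 and 61.92/48.0 = 1.29.
- Late BED: 105.6/90.0 = 1.17 and 122.4/90.0 = 1.36.

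**The case against.** The strongest reply is that nobody would plan from the table cell. The sentences just above it name the volume, define it and say how to draw it; an attending radiation oncologist does the contouring; and the literal reading conflicts with the GTV-PTV row at once. Table 2 is presented as an expansion guide, and the later pointer to it concerns margins, not the definition of the TGI. All this makes a misreading unlikely. It does not make the row correct.

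Second, the BED ratios compare target prescriptions before any step-down, not doses to gut. Stomach and duodenum must meet their limits under either reading; the step-down continues through the other volumes, and a patient whose plan still fails is removed. This stands and bounds the risk, all the more because section 8 names duodenal and gastric ulcers as the main serious toxicity. The protection is weaker for other small bowel and for large bowel, which the gut PRV includes but which have no numeric limit. That gap exists under either reading, but it makes the TGI rule the more specific safeguard for that bowel.

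Third, planning the TGI at 30 Gy may conflict with the goal that more than 90% of the PTV receive the full 3300 cGy, once the TGI exceeds about 10% of the PTV. The tension is real. It already exists under the protocol's own text rule, so correcting the row does not create it.

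Fourth, the table was read by machine and its header is collapsed. The TGI row still has its label, base structure, dose and expansion in order, and the other two rows read correctly, so a displaced cell is unlikely. The PDF can confirm this.

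**Conclusion.** The inconsistency is real: the TGI base structure in Table 2 is disjoint from the TGI in the text, and the text is the intended rule. It should be fixed. If the table were followed literally, target overlapping the gut PRV in Cohort B would be prescribed 3 or 6 Gy too much (10% or 20%), with early BED 14% to 29% higher and late BED 17% to 36% higher.

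This applies only to Cohort B patients whose targets overlap the gut PRV. Section 11.5 expects about 30 patients in Cohort B; the documents do not say how many would have overlap. Cohort A is prescribed 5 Gy × 5, so these doses do not describe it. No effect on the toxicity rate is shown, and nothing in the documents indicates that any plan followed the table.

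**What to change.** Reword the TGI row of Table 2 so that the base structure is (GTV-PTV or TVI-PTV) overlapping gut PRV, keeping 30 Gy (6 Gy × 5) and no expansion. Add one sentence stating that within the TGI the 30 Gy prescription replaces the 33 or 36 Gy prescription.

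Keep GTV-PTV and TVI-PTV as full structures. If the gut PRV were subtracted from them, the overlap that defines the TGI would vanish and the 25 Gy minimum would no longer cover it.

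The radiation oncology team should confirm the wording, and could say at the same time whether the TGI counts toward the 90% coverage goal. Checking the stored Cohort B plans for the definition actually used is an optional precaution.

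The required change is one table row and one sentence. Sample size, endpoint, stopping rule and analysis are untouched.

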Using the linear-quadratic formulation, the biologically equivalent dose (BED) of the two proposed fractionation schedules are given in comparison to other commonly used schemes (table 1), including conventionally fractionated radiation, which is typically administered in 28 1.8-Gy fractions for a total dose of 50.4 Gy, usually with concurrent capecitabine-, 5-FU-, or gemcitabine-based chemotherapy. While the BED for the 5 Gy x 5 schedule (early/late 37.5/66.7) must necessarily be lower because it will be used in patients who have already been treated with radiation to the pancreatic region, that of the proposed 6.6 Gy x 5 schedule (BED early/late 54.8/105.6) closely approximates that of standard chemoradiation (BED early/late 60/83.3), but without concurrent chemotherapy and treating a smaller tumor margin (0.3 cm vs. ~2 cm). Furthermore, the proposed 6.6 Gy x 5 fractionation schedule has a much lower late BED (105.6 vs. 233.3) with a similar early BED (54.8 vs. 87.5) as the previous 25 Gy x 1 regimen. Finally, the use of five-fraction SBRT regimens may be able to spare circulating lymphocytes from radiation-induced toxicity that is mediated by high radiation doses to circulating blood. As radiation-induced lymphopenia has been linked to inferior overall survival in patients with both unresectable and resectable pancreatic cancers, it is logical to explore potential ways to decrease the risk and severity of this toxicity. (22, 23) Circulating blood dose is directly proportional to radiation field size and fraction number, suggesting that SBRT is a potentially promising strategy to reduce the risk of radiation induced lymphopenia, perhaps leading to improved outcomes, in patients with pancreatic cancer.

Table 1. Comparison of Radiation Fractionation Schemes in Pancreatic Cancer.							
RT Dose	Regional Nodes	Concurrent	Early BED	Late BED			
(Gy)	Treated?	chemo?	(Gy)	(Gy)			
/# Fractions			$(\alpha/\beta = 10)$	$(\alpha/\beta = 3)$			
50.4/28	Yes	Yes	60 Gy	83.3 Gy			
30/10	Yes	Yes	39	60			
25/5	No	No	37.5	66.7			
33/5	No	No	54.8	105.6			
25/1	No	No	87.5	233.3			

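### Table 2 and the dose-reduction steps in Section 7.1.3 name no cohort and start from 30/33/36 Gy, which does not fit the 25 Gy prescription, the dose limits and the 20 Gy minimum given for re-irradiated Cohort A

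*Combined protocol and SAP*

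**What the plan says.** The prescription is split by cohort. Section 4.1 states: "Those patients who have received prior radiation therapy will constitute Cohort A and will receive SBRT as 5 Gy x 5". For the others it states: "Patients with no history of prior radiation treatment will constitute Cohort B and will receive SBRT as 6.6 Gy x 5". The Schema (Section 1) and Section 7.2 agree. Section 2.2 gives the reason: the biologically equivalent dose (BED) of the 5 Gy x 5 schedule "must necessarily be lower because it will be used in patients who have already been treated with radiation to the pancreatic region".

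Most limits in Section 7.1.3 are also split by cohort:

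- Gut: "No more than 1 cc of the proximal duodenum or proximal stomach may exceed 33 Gy for cohort B or 25 Gy for cohort A".
- PTV hot spot: at most 1 cc above 130% of prescription, printed as 4290 cGy for 6.6 Gy x 5 and "3250cGy for 5Gyx5, cohort A".
- PTV coverage: more than 90% of the PTV at full prescription, printed as 3300 or 2500 cGy.
- Minimum after reduction: GTV-PTV and TVI-PTV "must receive at least 25 Gy (20 Gy for cohort A").

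Two parts of the same section are not split. Table 2 assigns 30 Gy to the TGI, 33 Gy to the GTV-PTV and 36 Gy to the TVI-PTV, with no cohort label and no Cohort A row. The reduction sequence begins at those levels: "the dose to the TGI will first be decreased to from 30 to 25 Gy in 0.5 Gy increments". It then takes the GTV-PTV from 33 to 25 Gy, and the TVI-PTV in a similar way. The bullet closes with the minimum dose for both cohorts and with removal from protocol if it cannot be met.

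**The concern.** Table 2 is the only place that assigns a dose to each of the three target volumes, and the text refers to it without restriction. The reduction bullet starts from Table 2's levels and ends with a Cohort A minimum, so a planner would take it to govern Cohort A. Its starting levels, however, are all above what Cohort A is prescribed.

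The ambiguity concerns planned dose in previously irradiated patients, in a trial whose stated focus is safety. It also reaches the analysis in three ways:

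- Sections 11.3 and 11.9 pool the cohorts for the stopping rule and the primary toxicity estimate.
- Section 11.4 admits to the safety population only patients who received at least one SBRT session, so a patient removed at planning is not counted.
- Section 11.6 tabulates significant treatment-plan violations by cohort, which needs a single reference plan for each cohort.

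**Working it through.** **Step 1. Reproduce the plan's own figures.** Prescription = dose per fraction x 5.

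- Cohort A: 5 x 5 = 25 Gy. Cohort B: 6.6 x 5 = 33 Gy.
- Hot-spot limit at 130%: 1.30 x 33 = 42.9 Gy and 1.30 x 25 = 32.5 Gy. Both match the printed 4290 and 3250 cGy.

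**Step 2. Compare the Table 2 levels with each prescription and limit.**

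| Volume | Table 2 level | % of 25 Gy (A) | Above 32.5 Gy? | % of 33 Gy (B) | Above 42.9 Gy? |
|---|---|---|---|---|---|
| TGI | 30 Gy | 120% | no | 90.9% | no |
| GTV-PTV | 33 Gy | 132% | yes | 100% | no |
| TVI-PTV | 36 Gy | 144% | yes | 109.1% | no |

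The table is consistent with Cohort B and not with Cohort A.

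**Step 3. First reading: Table 2 applies to both cohorts.** Section 7.1.3 prescribes to the isodose line enclosing the whole PTV. At 33 or 36 Gy, any such volume larger than 1 cc in a Cohort A patient therefore breaks the 32.5 Gy limit. The 30 Gy TGI level is below that limit but above the 25 Gy that at most 1 cc of proximal duodenum or stomach may exceed in Cohort A. Whether it would break the gut limit depends on anatomy. The coverage line still gives 2500 cGy for Cohort A, so the same target would carry two doses.

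On this reading only, late BED = D(1 + d/3) would be:

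- 30 Gy: 30 x (1 + 6/3) = 90.0 Gy
- 33 Gy: 33 x (1 + 6.6/3) = 105.6 Gy
- 36 Gy: 36 x (1 + 7.2/3) = 122.4 Gy

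The Cohort A schedule gives 25 x (1 + 5/3) = 66.7 Gy. The formula reproduces the 66.7 and 105.6 in Table 1.

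**Step 4. Second reading: Table 2 is for Cohort B only.** Cohort A then has its overall 25 Gy prescription but no level for the TGI or the TVI-PTV. The written reductions are (30 - 25)/0.5 = 10 increments for the TGI and (33 - 25)/0.5 = 16 for the GTV-PTV. Both stop at 25 Gy, which is the full Cohort A prescription. The Cohort A minimum is 20 Gy, and no order or increment is written for the 25 - 20 = 5 Gy in between.

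**Step 5. Number of patients.** Section 11.5 expects about 6 Cohort A patients in a total enrollment of 38: 6/38 = 15.8% of the pooled denominator, if all are treated.

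**The case against.** The strongest reply is that Table 2 is plainly a Cohort B table with its label missing. It is titled as an expansion guide, and its GTV-PTV row shows the Cohort B schedule. The 5 Gy x 5 instruction for Cohort A appears repeatedly, and its limits and minimum are explicit. Section 7.1.3 also has a general rule to use the highest dose that meets the stomach and duodenal constraints, and a removal rule if the minimum cannot be met. An informed planner would not give Cohort A 36 Gy.

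Much of this stands. A reader might infer that the protocol directs 30 to 36 Gy for Cohort A. The documents do not support that: the universal scope is inferred from a missing label, and the excess-dose and BED figures in Step 3 hold only if the table is applied to that cohort. The reply does not close the gap, however. No sentence limits Table 2 or the sequence to Cohort B, and the Cohort A minimum sits inside the sequence. Accepting the Cohort B reading leaves the omissions in Step 4.

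Two other inferences should be set aside:

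- A reader might take 25 Gy as the Cohort A minimum. It is the general minimum; the Cohort A figure is 20 Gy.
- A reader might see a conflict in the duodenal constraints, because the general statement "following dose constraints must be met: V15< 9 cc, and V20< 3 cc" is followed by different Cohort A values (V12 < 9 cc and V15 < 3 cc). There is none. The volume receiving 15 Gy cannot exceed the volume receiving 12 Gy, so V12 < 9 cc implies V15 < 9 cc. In the same way, V15 < 3 cc implies V20 < 3 cc. The Cohort A limits are tighter and satisfy both statements.

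**Conclusion.** The inconsistency is real, and nothing in the documents resolves it. On one reading, two of the three Table 2 levels exceed the Cohort A hot-spot limit. On the other, Cohort A lacks two target levels and the reduction path to its own minimum. The prescription, the limits and the 20 Gy minimum are themselves clear. What is unclear is how a Cohort A plan is built up and stepped down, and so at what point such a patient is reduced or removed from protocol.

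The size is about 6 of 38 patients, if accrual follows Section 11.5. The documents give no basis for quantifying an effect on the toxicity rate. No sample size, confidence level or stopping boundary depends on this point. The conclusion assumes that Table 2 carries no cohort label in the source document, but it does not rest on the table alone, because the running text of the reduction sequence uses the same starting levels without a cohort split. No view is taken on which dose is right.

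**What to change.** State in Table 2, and in the reduction bullet of Section 7.1.3, which cohort each applies to. Reconcile both with the Schema, Section 4.1, the Cohort A limits in Section 7.1.3 and Section 7.2, so that each cohort has one consistent set of target-volume levels, reduction steps and minimum dose. The clinical team sets every value. The duodenal constraints need no change on this account.

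The cost is one protocol amendment, with the IRB approval that Section 13 requires, covering the table and the reduction text together; relabeling the table alone would leave the steps unresolved. No statistical section changes. If any Cohort A patients have already been planned, list the target levels and reductions actually used, so that the pooled toxicity estimate can be read with the delivered dose known.
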